8.3.2. Follow-up of subjects after adverse events

If an adverse event/adverse reaction occurs, the Investigator will institute support and/or treatment as deemed appropriate. If a non-serious adverse event/adverse reaction is unresolved at the time of the last visit, an effort will be made to follow up until the adverse event/adverse reaction is resolved or stabilized, the subject is lost to follow-up, or there is other resolution to the event.

9. STATISTICS

9.1. *Sample Size*

A sample size of 36 total completed subjects is needed for the study. Thirty-six completed subjects, who were originally randomized in a 1:1 ratio to the Nyxol 1% and the placebo groups, [REDACTED]

[REDACTED] Additionally, it is assumed that there will be approximately 10% drop-out between Baseline/Day 1 and Day 15. To account for this drop-out, a total of 40 subjects will be randomized into the study.

9.2. *Analysis Populations*

Full Analysis Set (FAS): The FAS will include all randomized subjects who have received at least 11 doses of study medication without missing 2 consecutive doses and have both a Baseline and a Day 15 IOP measurement. This population is also known as the Per Protocol (PP) population. The FAS will be used to analyze efficacy endpoints.

All Randomized Population (AR): The AR population will include all randomized subjects. This population is also known as the intent-to-treat (ITT) population. The AR population will be used in confirmatory efficacy analyses.

Safety Population (SP): The SP will include all randomized subjects who have received at least one dose of study medication. The SP will be used to summarize safety variables.

9.3. *Statistical Methods*

9.3.1. **General Considerations**

All continuous variables will be summarized by treatment and timepoint (as applicable) using descriptive statistics (n, mean, median, standard deviation, minimum, and maximum). All categorical variables will be summarized by treatment and timepoint (as applicable) using frequency counts and percentages.

All study data will be listed by treatment, subject and timepoint (as applicable).

All statistical tests will be performed using a significance level of 5% (two-tailed). Given the large number of secondary efficacy endpoints, the p-values for those analyses will be considered descriptive.

9.3.2. **Demographic and Baseline Characteristics**

Demographic and Baseline characteristics such as age, race, gender, and history of ocular surgery and procedures, will be summarized by treatment group using the FAS and the AR population. These data will also be provided in by-subject listings.

9.3.3. **Subject Disposition**

Subject disposition, including randomization, and completion and withdrawal from the study will be summarized using the AR population. These data will also be provided in by-subject listings.

9.3.4. Medical History and Prior/Concomitant Medications

Medical history will be coded using the latest version of Medical Dictionary for Regulatory Activities (MedDRA) and will be summarized by treatment group using the FAS.

Prior medications (medications with an end date prior to the date of randomization) and concomitant medications (medications with a start or end date after the date of randomization) will be coded using MedDRA and will both be summarized by treatment group using the FAS.

Medical history and prior and concomitant medications will also be provided in by-subject listings.

9.3.5. Analysis of Efficacy

Efficacy will be assessed using the FAS with subjects included in the treatment group they were randomized to, regardless of the treatment they actually received. For the analysis of the primary efficacy endpoint, observed case data will be used (no imputation will be performed for missing efficacy data) for the primary analysis. Confirmatory analyses will be performed using the AR population, with imputation performed for missing data. For the analysis of the secondary efficacy endpoints, only observed case data will be used. If warranted, confirmatory analyses using the AR population with imputation for missing data will also be performed for the secondary efficacy endpoints.

For all efficacy endpoints, Baseline is defined as the pre-dose value from the Baseline Visit/Day 1. If there is no pre-dose value from Day 1, then Baseline will be the value from the Screening Visit.

IOP will be measured twice in both eyes at each timepoint. The mean value at each timepoint for the study eye will be used in efficacy assessments. If the difference in the two IOP measurements is >5 mmHg, a third measurement will be obtained, and the three values averaged. The lighting conditions will be kept same from visit to visit.

Diurnal IOP is the mean of all three measurements (8AM, 10AM, and 4PM) on a specific day.

All efficacy data will be summarized by treatment group, study day and timepoint (8AM, 10AM, 4PM), as appropriate.

The primary efficacy endpoint is the change from Baseline to Day 15 in mean diurnal IOP. The primary efficacy endpoint will be analyzed using

Secondary efficacy endpoints (for the study eye unless otherwise noted) are indicated in Section 4.1.

For each of the continuous secondary efficacy endpoints, [REDACTED]

[REDACTED]

For each of the secondary efficacy endpoints related to percentage of subjects (or percentage of eyes) meeting certain criteria, the analysis will be performed using a logistic regression with treatment and Baseline included as independent factors. For each analysis, the percentage of subjects (or eyes) in each treatment group meeting the criteria, the odds ratio (OR) with 95% CI and p-value will be provided. For all of these endpoints, the FAS will be used with subjects included in their randomized treatment group regardless of the treatment they actually received.

9.3.5. Analysis of Safety

No statistical analysis of safety data will be performed in this study. Safety will be assessed using the SP with subjects included in the treatment group they actually received, regardless of their randomized treatment. Observed case data will be used; no imputation will be performed for missing safety data.

For all safety endpoints, Baseline is defined as the pre-dose value from the Baseline Visit/Day. If there is no pre-dose value from Day 1, then Baseline will be the value from the Screening Visit.

Biomicroscopy results, and ophthalmoscopy results will be summarized by treatment group using the SP. As both eyes are treated in the study; both eyes will be included in the summarizations for visual acuity, biomicroscopy, and ophthalmoscopy. Separate summary tables will be created for the study eye versus the fellow eye.

Heart rate and blood pressure values and change from Baseline in the values will be summarized by treatment group and timepoint (8AM on Day 8, Day 15 and Day 16; 4PM on Day 15).

Verbatim descriptions of AEs will be coded using MedDRA. Only treatment-emergent AEs (TEAEs; those that occur after the first dose of study medication *or increasing in severity after initiation of study medication*) will be summarized. TEAEs and serious AEs (SAEs) will be summarized by treatment group, by system organ class (SOC), severity, and relationship to study medication. Deaths, withdrawal from study medication due to AEs, and withdrawal from the study due to AEs will each be summarized by treatment group. Note that in MedDRA, ocular events are coded to the SOC of “special senses”. Thus, using SOC in the summaries will provide a separation of ocular and non-ocular adverse events.

All safety data will be provided in by-subject listings.

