#### **3.3. Summary of Statistical Analysis Changes to the Protocol**

The analyses described in this analysis plan are consistent with the analyses described in the study protocol.

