#### **4.2.2. Secondary Endpoints**

Secondary endpoints for efficacy and safety assessments include the following:

Efficacy:

Secondary efficacy endpoints will be analyzed by study eye, fellow eye and all eyes (the pooled data from the study eye and fellow eye) unless otherwise indicated, and will include:

- Change from Baseline to Day 15 in mean diurnal IOP in the fellow eye and all eyes.
- Change from Baseline to Day 8 in mean diurnal IOP.
- Mean IOP at each post-treatment timepoint (8AM, 10AM and 4PM; on Day 8 and Day 15).
- Change and percent change from Baseline to Day 8 and Day 15 in IOP at each timepoint (8AM, 10AM, 4PM), and Day 16 at 8AM.

- Percentage of subjects achieving reductions from Baseline to Day 8 and Day 15 in IOP at 8AM of greater than or equal to 10%, 15%, 20%, 25% and 30%.
- Percentage of subjects achieving Day 8, Day 15 and Day 16 IOP levels at 8AM of less than or equal to 16mmHg, 18mmHg, 20mmHg and 22mmHg.
- Change and percent change from Baseline Day 8, Day 15, and Day 16 in IOP at 8AM.
- Change and percent change to Days 8, 15, and 16 in pupil diameter at 8AM.
- Percentage of subjects achieving reductions from Baseline to Day 8, Day 15 and Day 16 in pupil diameter at 8AM, of greater than or equal to 10%, 15%, 20%, 25%, and 30%.
- Change from Baseline to Day 8, Day 15, and Day 16 in best corrected distance visual acuity (BCDVA) (Early Treatment Diabetic Retinopathy Study [ETDRS] high contrast) (photopic and mesopic) at 8AM.
- Change from Baseline to Day 8, Day 15, and Day 16 in distance corrected near visual acuity (DCNVA) (ETDRS high contrast) (photopic and mesopic) at 8AM.
- Percentage of subjects achieving improvements from Baseline to Day 8, Day 15, and Day 16 in BCDVA and DCNVA (photopic and mesopic) of greater than or equal to 1 line, 2 lines and 3 lines. For BCDVA, only the number of letters read is collected; this will be converted to lines as follows: 1 line = 3-7 letters read; 2 lines = 8-12 letters read; 3 lines = 13-17 letters read, etc. For DCNVA, only the logMAR value is collected; this will be converted to lines as follows: 1 line = 1.3 logMAR; 2 lines = 1.2 logMAR; 3 lines = 1.1 logMAR, etc. to 14 lines = 0.0 logMAR, 15 lines = -0.1 logMAR, 16 lines = -0.2 logMAR, and 17 lines = -0.3 logMAR.

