## 5.4. Analysis Variables

Variables to be summarized include demographics and baseline characteristics, medical (non-ocular) and ocular history, concomitant medications, and study drug accountability.

Efficacy variables include:

- IOP
- DCNVA (i.e., Near VA)
- BCDVA (i.e., Distance VA)
- Pupil diameter

Safety variables include:

- Conjunctival hyperemia (eye redness) measured with [REDACTED]  
[REDACTED]  
[REDACTED]  
[REDACTED]  
[REDACTED]  
[REDACTED]  
[REDACTED]  
[REDACTED]
- Biomicroscopy of anterior segment including evaluation of cornea, conjunctiva (other than redness) and anterior chamber. Fluorescein staining to be used.

- Ophthalmoscopy. Dilated fundus exam including optic nerve, macula, vessels and periphery.
- AEs
- Vital signs (HR and BP)
- Urine pregnancy tests for females of childbearing potential

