Secondary efficacy endpoints (for the study eye unless otherwise noted) are indicated in [Section 4.2.2](#). Secondary efficacy endpoints will be analyzed by study eye, fellow eye and all eyes (unless otherwise indicated). "All eyes" refers to the pooled data from the study eye and fellow eye, so there will be 2 results per subject for any summary of all eyes if the endpoint was assessed for both the study eye and fellow eye. Secondary efficacy assessments not related to IOP will be analyzed only at 8AM. Binocular near and distance VA assessments will not be analyzed. All secondary efficacy assessment data, regardless of whether they are included in the analysis, will be presented in by-subject listings.

For each of the continuous secondary efficacy endpoints, the same ANCOVA for the primary efficacy endpoint will be used, with the respective Baseline included as the covariate. Each ANCOVA will be performed using the FAS with subjects included in their randomized treatment group regardless of the treatment they actually received. The output from each ANCOVA will include the LSM and SE for both treatment groups, along with the placebo-corrected LSM (Nyxol – placebo), its 95% CI and associated p-value.

For each of the secondary efficacy endpoints related to percentage of subjects (or percentage of eyes) meeting certain criteria, the analysis will be performed for the FAS using a logistic regression with treatment and Baseline included as independent factors. For each analysis, the percentage of subjects (or eyes) in each treatment group meeting the criteria, the odds ratio (OR) with 95% CI and p-value will be provided.

For the analysis of the secondary efficacy endpoints, only observed case data will be used.

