## **10.3. Biomicroscopic and Ophthalmoscopic Examinations**

Results from biomicroscopic examinations, including conjunctival redness, cornea, conjunctiva (other than redness), anterior chamber, and corneal fluorescein staining will be summarized descriptively for each treatment group and overall by time point for the observed value. Results from ophthalmoscopic examinations, including optic nerve, macula, vessels and periphery will be summarized similarly. Separate summaries will be created for the study eye and the fellow eye.

For conjunctival redness, a descriptive summary of the numeric values from the CCLRU card 4-point scale will also be summarized by treatment group and overall by time point.

All examination data will be presented in by-subject listings. Unscheduled examinations will not be summarized but will be included in the listings.

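### The protocol names visual acuity in its safety summaries, but the readable SAP gives it no Safety Population summary and counts only measured gains, not losses.

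*Protocol*

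**What the plan says.** The safety analysis in Protocol 9.3.5 rests on the Safety Population: "Safety will be assessed using the SP with subjects included in the treatment group they actually received". Within that section, "both eyes will be included in the summarizations for visual acuity, biomicroscopy, and ophthalmoscopy", and separate tables are promised for study eye and fellow eye.

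SAP 5.4 lists near and distance acuity among the efficacy variables and leaves them out of the safety variables. SAP 10 covers adverse events, biomicroscopy and ophthalmoscopy, vital signs and pregnancy tests. SAP 10.3 carries over the two examinations that the protocol names beside acuity ("Results from ophthalmoscopic examinations, including optic nerve, macula, vessels and periphery will be summarized similarly"), but not acuity.

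SAP 4.2.2 makes acuity a secondary efficacy endpoint, analysed as mean change and as "Percentage of subjects achieving improvements from Baseline to Day 8, Day 15, and Day 16 in BCDVA and DCNVA" of at least 1, 2 and 3 lines. SAP 9.1 specifies the FAS for both the ANCOVA and the logistic regression, and adds: "Secondary efficacy assessments not related to IOP will be analyzed only at 8AM".

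SAP 3.3 reports no departure: "The analyses described in this analysis plan are consistent with the analyses described in the study protocol".

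**The concern.** Ocular safety against vehicle is a stated objective. The drug makes the pupil smaller (Protocol 2.2, Design justification), and acuity is tested with the lights on and off in people with glaucoma or ocular hypertension. Whether some subjects lose acuity is therefore a natural safety question, and the trial collects the data to answer it.

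Two features of the plan work against an answer. The responder tables count movement in one direction only. The set named for the models also leaves out some of the subjects in whom a visual problem would matter most: those who stop dosing early or have no Day 15 pressure reading.

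**Working it through.** This is mainly a comparison of texts. The one sample-size figure that can be rebuilt is the number randomised: 36 / (1 − 0.10) = 40, as stated. The point does not depend on it.

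**1. Where acuity sits**

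| Place | Role of acuity |
|---|---|
| Protocol 4.1 and 8.1 | Not among the safety measures or parameters |
| Protocol 9.3.5, Analysis of Safety | Named with biomicroscopy and ophthalmoscopy |
| SAP 5.4 | Efficacy only |
| SAP 8.3 | Baseline values, Safety Population and FAS |
| SAP 9.1 | Secondary efficacy; models in the FAS, 8AM |
| SAP 10 | Absent |

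From the readable SAP:
- Post-baseline acuity summaries stated for the Safety Population: 0.
- Categories of gain: 3 (at least 1, 2 and 3 lines).
- Categories of loss: 0.

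**2. Who is outside the FAS.** SAP 7.1.1 asks for at least 11 doses, no two consecutive doses missed, and both a Baseline and a Day 15 pressure. SAP 7.1.4 asks for one dose. There are 14 scheduled doses (Protocol 6.1). A subject who stops after 10 or fewer fails the dose count. One who stops after 11 or 12 has 3 or 2 doses left, and so fails the consecutive-dose rule if doses after stopping count as missed. Any subject without a Day 15 pressure is out regardless.

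**3. Early-termination values.** Protocol 4.9.4 and 7.2.8 ask that early leavers have a final visit with the Follow-up Visit examinations. Under Protocol 7.2.6 these include near and distance acuity. SAP 7.3.3 assigns early-termination data to a scheduled visit for safety variables only. Since SAP 5.4 does not class acuity as a safety variable, these values have no stated route into a table.

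**4. Illustrations (all inputs assumed, not taken from the documents).**
- Suppose 20 subjects per arm in the Safety Population and 18 in the FAS. If 2 Nyxol subjects lost at least 3 lines and both fell outside the FAS, a Safety Population count would show 2/20 = 10% and an FAS count 0/18.
- Suppose k of 18 FAS subjects each lose 15 letters. The mean change is zero if each of the others gains 15k / (18 − k) letters: 0.88 for k = 1, 1.88 for k = 2 and 3.00 for k = 3. In such a case the mean shows nothing, although the minimum would show a loss.

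**The case against.** Several strong points stand on the other side.

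- **Adverse events.** A reader might infer that vision loss is counted nowhere. The documents do not support that. Protocol 7.2.4 to 7.2.7 ask about eye problems at each contact after Baseline and have changes recorded as adverse events. SAP 10.1 tabulates these in the Safety Population, including events leading to withdrawal or to stopping study medication. What is missing is a count of measured loss, which does not depend on reporting.
- **Mean change.** A reader might also infer that the acuity analyses can show only benefit. They can show harm: the ANCOVA is two-sided with a 95% confidence interval, and SAP 7.4.1 includes the minimum and maximum. All acuity data are listed by subject.
- **Thin protocol basis.** The quoted sentence mainly says which eyes are summarised. The sentence before it names the Safety Population for biomicroscopy and ophthalmoscopy only, and the protocol's own safety lists omit acuity. The protocol never planned counts of lines lost, so that part is an addition and not a dropped analysis. Even so, the protocol's safety section does name acuity, and the SAP neither carries this over nor explains the omission.
- **8AM only.** This is no departure, because the protocol's acuity change endpoints are themselves set at 8AM. Acuity is also measured at 4PM on Day 15 (Protocol 7.2.5), but Baseline acuity is taken at 8AM only (Protocol 7.2.3), so a 4PM change has no time-matched baseline.
- **Other populations and redaction.** SAP 9 names the FAS, all-randomised and per-protocol sets for efficacy unless otherwise noted, whereas SAP 9.1 specifies the FAS for these models. Running them in the all-randomised set would still count gains only. The planned-table list is redacted and may contain an acuity table for the Safety Population.

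**Conclusion.** The point holds in a limited form. Followed as readable, the plan gives no count of measured acuity loss and no stated table for acuity measured at an early-termination visit. It does not reconcile this with the protocol's mention of acuity under safety. That narrows what the trial can say on its own ocular-safety objective.

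The size cannot be put in numbers from the documents. They give no standard deviation for acuity change and no expected rate of loss. The planned drop-out of about 4 of 40 (10% × 40) is from all causes and is not an estimate of subjects with visual loss. The conclusion assumes that the redacted table list adds no Safety Population acuity summary. The change is worth making before unmasking, but it does not affect the primary analysis.

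**What to change.** Add a subsection to SAP 10, descriptive only, in the Safety Population as treated:

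- Monocular BCDVA and DCNVA, photopic and mesopic, as observed values and change from Baseline, by arm, for study eye and fellow eye separately, at each visit.
- The number and percentage losing at least 1, 2 and 3 lines from Baseline by arm, under the same line definition as for gains.
- Early-termination acuity values, with SAP 7.3.3 extended to cover them.
- Day 15 4PM acuity as observed values, or as change clearly labelled as being from the 8AM Baseline.

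Reconcile Protocol 4.1, 8.1 and 9.3.5 with SAP 5.4 and 10 on whether acuity is a safety measure. If the sponsor prefers not to add the summary, SAP 3.3 should declare and justify the omission.

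The cost is SAP wording and a few extra descriptive tables from data already collected. No new assessments or tests are needed.

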9.4. Procedure for accounting for missing, unused, or spurious data

For the summarization and analysis of efficacy data, the focus will be on observed case data only. No imputation will be performed for missing data. As appropriate, confirmatory efficacy analyses will be performed using imputation for missing data;

details of the imputation will be included in the study Statistical Analysis Plan. For the summarization of safety data, observed case data only will be used.

9.5. Procedure for reporting deviations from the statistical plan

Any deviations from the statistical plan will be described and a justification given in the final Clinical Study Report (CSR).

10. DIRECT ACCESS TO SOURCE DATA AND DOCUMENTS

The Investigator will permit study-related monitoring visits, audits, IRB review, and regulatory inspection(s) by providing direct access to source data and documents.

11. QUALITY CONTROL AND QUALITY ASSURANCE

The progress of the study will be monitored by on-site, written, and telephone communications between personnel at the Investigator's site and the Medical Monitor. The Investigator will allow Ocuphire, the Study Monitor, and the Medical Monitor to inspect all CRFs, subject records (source documents), signed consent forms, records of study medication receipt, storage, preparation, and disposition, and regulatory files related to this study.

12. ETHICAL CONSIDERATIONS AND GCP COMPLIANCE

12.1. GCP compliance

The proposed study is subject to all applicable governmental rules and regulations concerning the conduct of clinical trials on human subjects. This includes, but is not necessarily limited to, the approval of Institutional Review Boards, the Helsinki Declaration, U.S. FDA Law, ICH GCP guidelines, obtaining prospective informed consent, monitoring of the conduct of the study and the completeness of the CRFs by Ocuphire or its designee(s), and appropriate record retention by the Investigator.

12.2. Institutional Review Board (IRB)

This protocol, materials used to recruit subjects, and materials used to document consent must be approved by the IRB prior to initiation of the study. Written IRB approval must adequately identify the protocol and informed consent. In addition to approving the protocol, the IRB must also approve the Subject Information and Consent Form, as well as any advertising tools that will be used for the study. Written approval also must indicate whether approval was granted based on full committee review or expedited review. Copies of all approved materials, all correspondence with the IRB and written approval from the IRB must be made available to Ocuphire, *prior* to the start of subject enrollment into the study.

